12.2.2. Economic report of the trial

All the necessary additional material is paid by the promoter and principal investigator of this clinical trial. That is, the coverage of the sphygmomanometers, seed sacks, temperature thermometer, portable countdown timer, camera, stationery and toner.

As well as the training of nurses, collaborators / observers and the acquisition of the Photoshop program and statistical package SPSS version 23.

No economic goods or economic budget for the material resources by external to the investigation are contemplated.

13. PRACTICAL CONSIDERATIONS

13.1. Training of the nursing team and collaborators / observers

It is considered necessary to train the nursing team with certain scales that, except for the VAS / Numeric scale, are not commonly used in routine clinical practice. Likewise, interventions require specific knowledge a priori.

No training is contemplated, because the nurses are familiar with the material resources they will use, only a training is planned with the possibility of asking questions and these will be solved and / or clarified. The main researcher will belong to the collaborating nursing team and will support them in the fieldwork.

Similar situation is that of collaborators / observers of the intensity of hemolysis. Those involved in the evaluation of blood samples will be trained, although they are trained in the use of the material involved.

13.2. File of the documentation

Throughout the study, a file is created with all the documents involved throughout this essay. At least the following will be included:

- CEIm report
- Information sheet and informed consent.
- This protocol, as well as its amendments; in which case.
- Any correspondence with the CEIM.
- Registration of signatures of the collaborating nursing team.
- Any document related to the acceptance of the viability of the project in the institution.
- Serious adverse events notification form
- Registration of the reversible coding of subjects.
- CRF copies

The results of the CRF are considered complete at the time of venipuncture. It has been considered appropriate to carry out two CRFs, with the completion of workfield of fusion, due to the need for the evaluation of hemolysis. In this way, it is intended to complete the CRFs in two different work rooms: CRF for hemolysis in the laboratory and those corresponding to venipuncture in the phase I room; Avoiding the violation of blinding.

It is estimated that once the study was completed, a place where the personal data of the subjects were recorded was saved and saved, under the same conditions as those reflected in section 12.1.5.

13.3. Terms of results publication

Once the fieldwork is completed, the data will be irreversibly dissociated and therefore anonymized data will be obtained. It is considered irreversible when establishing the link between a data and the subject to which it refers is no longer possible by reasonable means (2,62).

Only information that is anonymous can be transferred to third parties (62).

13.4. Amendments to the protocol

When amendments to the protocol are made, they will be notified their evaluation and subsequent opinions.

14. STATISTICAL ANALYSIS PLAN

14.1. Main analysis

14.1. 1. Definition of variables

Primary variable

Successful venipuncture at the first attempt. Dichotomous qualitative variable. Success / Failure

Secondary variables

Successful venipuncture frequency. Discrete quantitative variable. (1,2,3,4)

Visual intensity of hemolysis. Discrete quantitative variable. It is measured in stadiums.

Scale of expressed pain intensity (VAS). Discrete quantitative variable.

Scale skin types Fitzpatrick. Discrete quantitative variable.

Ingestion of liquids (less than 500 ml) in the last 6-8h prior to cannulation. Discrete quantitative variable (measured in glasses); it will be transcribed continuously for statistical analysis.

Affiliation of individuals

Respected fasting of 6-8 hours. Dichotomous qualitative variable.

Age. Quantitative variable continues.

Sex. Dichotomous qualitative variable.

Race. Discrete quantitative variable. 1 -> Caucasian 2 -> Black 3 -> Asian 4 -> Latin

BP. Continuous quantitative variable.

HR. Continuous quantitative variable.

T. Continuous quantitative variable.

BMI Continuous quantitative variable.

14.1. 2. Sample size calculation

The sample calculation is performed with the GRANMO calculator (63). It assumes a random risk (alpha) of 5% and a statistical power (beta) of 80%; for which it is tried to prove the veracity of the null hypothesis, of bilateral type.

That is, the risk of rejecting the null hypothesis when this is true is 5%, and the probability of not rejecting it being false is 20%.

In the literature, the success of peripheral intravenous canals was recorded in the first attempt, using the usual technique, in 74% of the cases (55). Currently, a proportion of peripheral intravenous cannulation has been registered at the first attempt of 73%, in an ultrasound ecoguided manner (33). In relation to the second successful attempt, in the usual clinical practice it amounts to 92% of the cases and, in the ultrasound ecoguided to 91% (33.55).

For the present work we intend to achieve a 95% success rate in antebrachial venous cannulation at the first attempt. Thus, overcome with one of the alternative methods proposed in this study the cumulative proportion of the second attempt of the usual and eco guided clinical practice.

It is considered a clinically relevant difference the successful venous cannulation at the first attempt when, not only allows the cannulation at the first attempt of those cases that hypothetically would be observed, but accumulate to those cases that, in a way observed in the literature, the cannulation has been achieved at the second attempt, and hypothetically, that success can be achieved in the first attempt.

The comparative indicators are based on the comparison method and the reduction of intraindividual variability. It is considered a root of the experience, one of them is lost; An average of both percentages has been made, thus obtaining a 12% loss approximately.

Therefore, the calculation of the sample size should be followed through the modality of proportions, paired measures (repeated in a group). Fix in the proportion with pre-intervention event 0.74, in the proportion with post-intervention event 0.95, and the loss ratio 0.12.

Finally, the estimated sample size is 60 subjects.

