14.1.3.1.2. MULTIVARIATE STATISTICS

Therefore, it is considered pertinent to perform a logistic regression, multivariate statistics. The primary variable is assumed as the dependent variable and the secondary variables as returnable or explanatory. The primary variable fulfills the requirement of being dichotomous and the return variables assume any type of variable. It is assumed the need to create dummy variables with alternative methods, whose reference will be the comparator.

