14.3. Secondary analysis attached

It has been considered that the approach of non-main secondary objectives could be carried out through the following methodology:

To identify the effectiveness of all the methods used in antebrachial venipuncture, in what refers to venipuncture at the first attempt.

It is intended to be addressed by means of a logistic regression, at the same time as the multivariate statistics for the main variable.

To evaluate the intensity of hemolysis of the blood samples, in what refers to the applied method, respectively.

It is considered that there is enough information on this subject to use a parametric test. In this case, the intensity of hemolysis is the dependent variable, it is considered justified to use an ANOVA test of a block test.

Identify the frequency of successful venipuncture at the first attempt and analyze if there is an association between it and the demographic characteristics of the individuals.

It is intended to be addressed through descriptive statistics. To analyze the association, a logistic regression will be performed; multivariate technique.

Analyze the correlation between methods used, intensity of hemolysis and pain.

It could be considered that enough information is known about pain to use parametric techniques, it is supposed to be the dependent variable and it is discrete. Therefore, it is intended to be approached using the ANOVA statistical technique or two-way F-test without interaction.

Identify and quantify adverse events, as well as their relation to skin types.

For the identification and quantification, a descriptive statistic will be carried out. In order to assess the possible association, using the Fitzpatrick scale, it is considered that there is not enough information about its distribution, so it is considered appropriate to use a nonparametric type test; the Kruskal-Wallis test.

14.4. Intermediate analysis.

Does not apply.

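### Race, a nominal factor, is declared a quantitative variable coded 1 to 4, and its coding in the demographic logistic regression is not stated

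*Combined protocol and SAP*

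**What the plan says.** Section 14.1.1 lists the variables with a type for each. Among the subject characteristics it gives "Race. Discrete quantitative variable. 1 -> Caucasian 2 -> Black 3 -> Asian 4 -> Latin". The entry just before it reads "Sex. Dichotomous qualitative variable", and respected fasting is typed the same way, so the list does separate qualitative from quantitative variables.

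The outcome is "Successful venipuncture at the first attempt. Dichotomous qualitative variable. Success / Failure". Section 5.2.2 makes its association with demographic characteristics a secondary objective. For that objective section 14.3 plans descriptive statistics and then states: "To analyze the association, a logistic regression will be performed". It gives no coding rule for the covariates.

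The one coding instruction is in section 14.1.3.1.2, on the main logistic model: "It is assumed the need to create dummy variables with alternative methods, whose reference will be the comparator". On the other explanatory variables the same section says that "the return variables assume any type of variable".

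**The concern.** A quantitative covariate in a logistic regression gets one coefficient: the change in log-odds per unit. For race coded 1 to 4 this means equal steps from Caucasian to Black to Asian to Latin. The order and spacing come only from the numbering, so the odds ratio per step has no meaning, and another numbering of the same data gives another result.

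At stake is the race result within one stated secondary objective. An analyst who follows the declared type would report an odds ratio that nobody can interpret. It could be null when groups differ, or it could suggest a gradient across groups that are alike.

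**Working it through.** The plan gives no figure on this point to reproduce. It also gives no racial mix and no success rate by race, so every mix and rate below is an assumption made for illustration. From the documents come the codes 1 to 4, the 60 subjects (14.1.2) and the two-sided 5% level (14.1.2). Each subject is counted once.

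**1. A difference the slope cannot see.** Assume 15 subjects per group and success of 0.80, 0.60, 0.60, 0.80 in codes 1 to 4. Mean success is 0.70 and the mean code is 2.5. The score for the slope is Σ n(x − 2.5)(p − 0.70) = 15 × [(−1.5)(0.10) + (−0.5)(−0.10) + (0.5)(−0.10) + (1.5)(0.10)] = 15 × [−0.15 + 0.05 − 0.05 + 0.15] = 0. The fitted odds ratio per step is exactly 1.00.

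**2. What indicator coding would detect for that pattern.** For the 3-df likelihood-ratio test the noncentrality is λ = 2 Σ n[p ln(p/0.70) + (1 − p) ln((1 − p)/0.30)].
- At p = 0.80 the bracket is 0.1068 − 0.0811 = 0.0257.
- At p = 0.60 it is −0.0925 + 0.1151 = 0.0226.
- λ = 2 × (30 × 0.0257 + 30 × 0.0226) ≈ 2.90.
- Against the critical value 7.81, power is about 27%. With an assumed mix of 30/6/6/18 it is about 19%.

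**3. Dependence on the numbering.** Assume 15 per group and success of 0.90/0.60/0.60/0.90. The numeric model was fitted to the expected counts, and only the numbers given to the four groups (in that order) were changed:

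| Numbers given to the four groups | Odds ratio per step | p |
|---|---|---|
| 1, 3, 4, 2 | 0.50 | 0.022 |
| 1, 2, 3, 4 | 1.00 | 1.0 |
| 3, 1, 2, 4 | 2.01 | 0.022 |

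**4. A false gradient.** Assume 15 per group and success of 0.95/0.95/0.95/0.60, so that only group 4 differs. The fit to expected counts gives an odds ratio of about 0.33 per step (simulated median 0.30). The model then implies an odds ratio of about 0.33² ≈ 0.11 between groups 3 and 1, whose success rates are in truth equal.

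**5. Rejection rates.** Simulated, N=60, 1,000 runs per row, likelihood-ratio tests at 5%:

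| Success in codes 1–4 | Mix | Race as a number (1 df) | Three indicators (3 df) |
|---|---|---|---|
| 0.85 in all | 15/15/15/15 | 4.6% | 6.9% |
| 0.85 in all | 30/6/6/18 | 6.7% | 4.1% |
| 0.90/0.60/0.60/0.90 | 15/15/15/15 | 1.0% | 69% |
| 0.90/0.60/0.60/0.90 | 30/6/6/18 | 3.5% | 48% |
| 0.95/0.60/0.95/0.95 | 15/15/15/15 | 5.5% | 79% |
| 0.95/0.60/0.95/0.95 | 30/6/6/18 | 1.1% | 48% |
| 0.95/0.95/0.95/0.60 | 15/15/15/15 | 73% | 78% |
| 0.95/0.95/0.95/0.60 | 30/6/6/18 | 78% | 81% |

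The first two rows show no systematic inflation from numeric coding when race has no effect. The last two show that it loses little power when the group that differs happens to sit at the end of the code order.

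**The case against.** The plan never says that race enters the model as a number, and its type labels are a poor guide to model form. Section 14.2.1 types the observers and the blood samples as discrete quantitative, and CMYK colorimetry as both continuous and qualitative. The label on race may be a slip that a competent analyst would override. This stands as a caution: a reader might infer that a linear trend will certainly be fitted, and the documents do not go that far.

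A reader might also infer from 14.1.3.1.2 that indicators are reserved for the methods. That too goes beyond the text. The sentence names the methods and their reference but excludes nothing. It belongs to the main model, for which "The primary variable is assumed as the dependent variable and the secondary variables as returnable or explanatory", and race is not in the list of secondary variables. If anything, it shows that the authors know nominal factors need indicators.

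Finally, the zero slope comes from a chosen symmetric pattern with equal groups, and the recommended coding would itself miss that pattern about 73% of the time at N=60. This stands as well.

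None of these points supplies a correct coding for race. The only statement the document makes about race as a variable gives it the wrong type.

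**Conclusion.** The point holds as a minor one. Section 14.1.1 gives race the wrong type, and the demographic regression in 14.3 does not correct it. Followed as written, the plan yields one odds ratio per code step that depends on arbitrary numbering: 0.50, 1.00 or 2.01 from the same assumed data.

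Two stronger readings are not supported. The first is that numeric coding creates associations out of nothing. With no race effect it rejected in 4.6% to 6.7% of simulated trials, against 4.1% to 6.9% with indicators. What it can produce is a false ordering once some group truly differs. The second is that indicators would reliably find a 20-point difference. They have about 27% power for it with equal groups and about 19% with the uneven mix. The higher figures of 48% to 81% belong to differences of 30 or 35 points.

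The gain is therefore an interpretable estimate in one non-main secondary analysis. The McNemar test, the sample size and the intervention comparisons do not depend on it. The illustrations rest on assumed mixes and rates; the dependence on code order does not.

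**What to change.** In 14.1.1, redefine race as a nominal qualitative variable and note that the codes are labels only. In 14.3, state that race enters the demographic logistic regression by indicator variables with the largest group as reference, and that it is collapsed to two groups if cells are sparse. Fix the rule for sparse cells before the data are seen.

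The cost is a line or so in each section. Three indicators replace one slope, so there are at most two extra parameters, and none if race is collapsed to two groups. Data collection does not change. The downside is imprecise estimates for small groups, which should be reported with their confidence intervals.

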2.11. Hypothesis and main goal

Hypothesis. The number of attempts of success venipuncture at first time are influenced by any of the interventions applied before.

Main goal. To identify the most effective intervention of applying dry local heat and/or high tourniquet pressure in relation of number success venipuncture attempts, compared to current clinical practice.

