5. HYPOTHESES AND OBJECTIVES

5.1. Hypothesis

The frequency of cases in successful antebrachial venepuncture at the first attempt is affected by the applied method.

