5.2. OBJETIVES

5.2.1. Main objective

To identify the best effectiveness of the application of topical heat and / or high stagnation pressure in successful antebrachial venipuncture at the first attempt; Regarding the usual practice so far.

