5. CA + P -> C. Combination of dry topical heat and high stagnation pressure in the first period. Comparator in the second period.

6. C-> PA + C. Comparator in the first period. Combination of dry topical heat and high stagnation pressure in the second period.

As a result of these options and the coverage of the Clinical Trials Unit of the University Hospital of La Princesa is twelve individuals in each group, the following sealed envelopes for each group are established

- Four contain topical heat and comparator intervention

- Two will be topical first period heat. Comparator in the second -> [CA-> C]
- Two will be comparator in the first period. Topical heat in the second -> [C-> CA]

- Four intervention of high pressure and comparator

- Two will be high pressure in the first period. Comparator in the second -> [P-> C]
- Two will be comparator in the first period. High pressure in the second -> [C-> P]

- Four combined (topical heat and high pressure) and the comparator

- Two will be combination in the first period. Comparator in the second -> [CA + P-> C]
- Two will be comparator in the first period. Combination in the second -> [C-> CA + P]

This scheme of twelve envelopes will be carried out five times to address a sufficient sample size, of sixty subjects, to assume the estimated losses and, finally, to obtain the number of subjects, who have completed both periods, calculated to obtain a statistical significance of the results.

Due to the inclusion / exclusion criteria established, and which will result from the first evaluation VIA (36), an equivalent number of individuals in each arm will be sought.

In each envelope, the chronological order of application of the intervention-comparator will be included, by default and without previous knowledge.

It will be randomized only once, in the first period. In the second period, the remaining sequence will be applied. Figure 1

[figure not shown]

Figure 1. Design flow diagram. Own elaboration.

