10.2. Global effectiveness reach

10.2. 1. Clinically relevant parameter in venipuncture

An optimal effectiveness for venipuncture at the first attempt will be considered reached when one of the three interventions manages to overcome the success rate at the first attempt through usual clinical practice. That is, when a success rate of more than 74% is achieved (55).

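### The stated 80% power covers only the single pooled McNemar test with the three interventions averaging about 95%; it does not cover the one-method target or the main objective of finding the best method

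*Combined protocol and SAP*

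**What the plan says.** **Sample size.** Section 14.1.2 uses two-sided alpha 5%, power 80% and the calculator's option for paired proportions in one group: "Fix in the proportion with pre-intervention event 0.74, in the proportion with post-intervention event 0.95, and the loss ratio 0.12". The result is: "Finally, the estimated sample size is 60 subjects". Section 2.13 repeats the 80% but attaches it to 54 subjects to be enrolled, and 9.9 ends fieldwork at subject number 54.

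**Target.** The same section 14.1.2 explains the 95% as the aim to "overcome with one of the alternative methods proposed in this study the cumulative proportion of the second attempt".

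**Question asked.** The main goal in 2.11 is "To identify the most effective intervention of applying dry local heat and/or high tourniquet pressure in relation of number success venipuncture attempts", and 5.2.1 agrees: "To identify the best effectiveness of the application of topical heat and / or high stagnation pressure". The effectiveness criterion in 10.2.1 is met when "one of the three interventions manages to overcome the success rate at the first attempt through usual clinical practice". The hypothesis in 5.1 is collective: "The frequency of cases in successful antebrachial venepuncture at the first attempt is affected by the applied method".

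**Allocation.** Each subject receives one of the three interventions plus the comparator. In each block of twelve envelopes in 6.3, "Four contain topical heat and comparator intervention", with four each for pressure and for the combination; the block is used five times.

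**Analysis.** Section 14.1.3.1.1 applies one McNemar test to the calculated sample, with the alternative methods taken together, and raises the best-method question after a significant result. Section 14.1.3.1.2 plans a logistic regression with method dummies against the comparator. Sections 14.1.3.2.2 and 14.3 plan per-method odds ratios and the same regression without making them conditional on the pooled test.

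**The concern.** The only power figure for the primary variable belongs to the question of whether the interventions, taken together, differ from the comparator. The main goal, the main objective, the 95% target and the effectiveness criterion are all framed per method. A reader of 2.13 or 14.1.2 would take the 80% to apply to them.

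Two misreadings could follow. If one method works and the others do not, the pooled test dilutes the effect, and a non-significant result could be taken to mean that no method helps. If one method's own comparison is non-significant on about 18 pairs, that could be taken as evidence against it. The plan does not say how per-method results will be presented if the pooled test is not significant.

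**Working it through.** **Inputs from the documents.** Comparator 0.74, intervention 0.95, so d = 0.21; loss 0.12; two-sided 5%; power 80% (14.1.2). Allocation 4:4:4 per twelve, five blocks (6.3), so 20 per method; 20 × 0.88 = 17.6, about 18 pairs. In total, 60 × 0.88 = 52.8, about 53 pairs.

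**Input not in the documents.** The within-subject correlation, or equivalently the discordant proportion pd. With margins 0.74 and 0.95, pd can run from 0.21 (no subject succeeds with the comparator and fails with the intervention) to 0.31 (no subject fails both). Independence is an assumption made here: p01 = 0.26 × 0.95 = 0.247, p10 = 0.74 × 0.05 = 0.037, pd = 0.284.

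**1. The plan's 60.** n = (1.96√pd + 0.8416√(pd − d²))² / d².

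- Independence: n = 48.1. Adding 1/d as a continuity correction gives 52.9, and 52.9 / 0.88 = 60.1. Without the correction, 48.1 / 0.88 = 54.7.
- Maximum discordance (0.31), no correction: n = 52.75, and 52.75 / 0.88 = 59.9.

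Both routes give about 60, so the result does not reveal which input was used. Either way, 60 is the total for one paired test on every subject.

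**2. Pooled test at 53 pairs.** Full enumeration of discordant counts, independence. The pooled cells are averages over the three methods; for 95/74/74 the mean is 0.81, so p01 = 0.26 × 0.81 = 0.2106 and p10 = 0.74 × 0.19 = 0.1406.

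| True success of the three methods | Exact McNemar | Uncorrected McNemar |
|---|---|---|
| 95/95/95 | 82% | 87% |
| 95/90/90 | 60% | 68% |
| 95/74/74 | 9% | 14% |

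For 95/95/95 at maximum discordance the figures are 77% and 83%. For 95/74/74 with all 60 subjects they are 10% and 15%, under independence.

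**3. One method against its own comparator period, 18 pairs, 95% v 74%.** This is an illustration; the plan contains no such test.

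| pd | Exact | Uncorrected | 95% CI half-width, 1.96√((pd − d²)/18) |
|---|---|---|---|
| 0.21 | 16% | 54% | 18.8 points |
| 0.284 (independence) | 17% | 41% | 22.6 points |
| 0.31 | 17% | 37% | 23.8 points |

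The half-width is therefore about 19-24 points, against a targeted difference of 21.

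**4. The planned logistic model**, approximated as 18 method attempts against 53 comparator attempts, ignoring pairing and covariates: power about 61% by likelihood ratio and 38% by Fisher's test. An arm truly at 95% has no failures among 18 with probability 0.95¹⁸ = 0.40, and its odds ratio is then not estimable.

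**5. Picking the best method**, 18 per arm: the truly best arm is observed strictly highest with probability about 91% at 95/74/74 and 41% at 95/90/90.

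**6. 54 and 60.** 60 × 0.88 = 52.8; 54 / 60 = 0.90, a 10% loss. Neither 2.13 nor 9.9 says that 54 means completers.

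**The case against.** The strongest reply is that the calculation contains no error. The hypothesis in 5.1 and the McNemar test in 14.1.3.1.1 are collective, 60 is right for them, and powering one confirmatory test before estimating per-method effects is a common design. That stands: a reader might infer that 60 was miscalculated, and it was not. What it leaves open is that 14.1.2 itself ties the 95% to one method, while the pooled test needs an average of about 95% across all three.

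A reader might also take 17-41% as the power of the main objective. The documents do not support that. No per-method McNemar test is planned; the planned model borrows all comparator attempts and does better. Nor is power against the comparator the chance of picking the best method, which is high when one method stands out and poor when the methods are close.

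A third tempting reading is that the protocol assumed independent attempts. It states no correlation, and maximum discordance without continuity correction gives about 60 as well.

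On 54 against 60, section 6.3 goes far to explain the gap: sixty are taken to absorb losses and leave enough subjects who complete both periods. What remains is that 2.13 speaks of enrolling 54 and 9.9 stops at subject 54. The per-method odds ratios in 14.1.3.2.2 and 14.3 already supply part of the reporting requested below.

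**Conclusion.** The point holds as one of scope; the arithmetic of the 60 is sound. The 80% applies to the pooled McNemar test on all subjects, and only if the interventions average about 95% against 74%. If one method alone reaches 95% and the others match the comparator, that test has about 9-14% power (53 pairs, independence assumed). With about 18 pairs per method, the power approximations in the working for a single method against the comparator at 95% v 74% all fall below 80%, and the paired difference would carry a margin of about 19-24 points. The documents state no power or precision for the main objective.

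The pooled and logistic figures rest on independence or on ignoring pairing; the per-method McNemar power and interval widths are shown over all feasible discordance. It does not follow that the trial must be enlarged: the plan can keep its size if it says what that size supports. This should be fixed before the results are read.

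**What to change.** 1. **Sections 14.1.2 and 2.13.** State that the 80% refers to the pooled McNemar test with the interventions averaging about 95% against 74%. The sponsor should state the discordance or correlation entered in the calculator; independence should not be written in unless it was used. Give the per-method size (20 randomised, about 18 pairs) and the expected 95% CI half-width for the paired difference (about 19-24 points). Describe identification of the best method as estimation, not covered by the 80%.

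2. **Section 14.1.3.1.1.** Report each intervention against its own comparator period as a paired difference with a 95% CI, whatever the pooled p-value. Present these as estimates alongside the planned odds ratios, noting that an odds ratio may not be estimable when an arm has no failures.

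3. **Sections 2.13 and 9.9.** Reconcile 54 with the 60 in 6.3 and 14.1.2, say whether 54 means completers of both periods, and align the end of fieldwork with that.

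Cost: protocol and SAP wording only, with no extra subjects and no further confirmatory tests. The downside is a less favourable stated power for the main objective.
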